13.7.2 Independent Safety Monitor (ISM)

Physicians serving on the Clinical Direction SOC and who are not affiliated with a clinical site will serve as ISMs to review RAEs reported to the CCC on a rotating basis. Other members on the Clinical Direction SOC will also serve as an ISM when necessary, but cannot review events from their clinical site. When a RAE is identified by a clinical site the information will be redacted to conceal treatment assignment, reported to the CCC, and then forwarded to the on-call ISM to make a determination. The ISM will be responsible for:

- Reviewing reports of RAEs;
- Confirming or refuting classification of the event as an RAE;
- Making a determination about relatedness of the RAE;
- Requesting additional information as needed in order to make a determination;
- Providing the CCC with follow-up reports for ongoing RAEs as new information becomes available; and
- Notifying the CCC of the final status for the event once it has been determined.

13.8 Reporting Expected AEs and RAEs to the DSMB

The DSMB will review tabulated data on non-serious and expected AEs on a semi-annual basis and monitor for adverse event rates out of proportion to those expected. The CCC will forward the individual Reportable Adverse Event Records, including a narrative for each event, as well as a table showing all RAEs to the DSMB and NIA semi-annually. The DSMB will review all RAEs that are temporally related to the interventions in aggregate form at its scheduled meetings.

All RAEs that relate to hazards of the study interventions or are cause for urgent concern will be reported to the CCC and the CCC will report these to the DSMB chairman, NIA, and the UMB IRB immediately after recognition of their importance. If the DSMB chairman concludes that an RAE is of universal and immediate concern, the CCC will notify local clinical sites at once. The DSMB chairman may recommend convening the DSMB to review participant safety based on any individual report or accumulating evidence, including evidence according to treatment assignments.

Section 14: Intervention Discontinuation

Certain RAEs may result in a temporary interruption or early discontinuation of the trial assessments and interventions or components of these assessments and interventions. Please refer to the appropriate MOP chapter(s) for specific instructions on stopping criteria during screening, intervention, and follow-up assessments.

After such RAEs occur, a participant may resume the trial intervention when the clinical site clinician and the primary care provider (if participant has one) agree that it is appropriate. For mild problems that require temporary cessation of intervention, the clinical site investigator, in consultation with the clinical site clinician and participant, may agree to reintroduce the participant to the study intervention.

At any time, the DSMB may recommend discontinuation of any component or intervention group of the study for any of the following reasons:

- 1) Compelling evidence from this or any other study of an adverse effect of the study intervention(s) that is sufficient to override any potential benefit of the interventions to the target population.
- 2) Compelling evidence from this or any other study of a significant beneficial effect of the study intervention(s), such that its continued denial to other study group(s) would be unethical.
- 3) A very low probability of addressing the study goals within a feasible time frame.

Section 15: Data Analyses

Analyses for all aims will be performed according to the intention-to-treat (ITT) paradigm. Prior to confirmatory analysis, exploratory data analyses will be performed. These exploratory analyses will consist of histograms for continuous outcomes to examine whether a transformation is needed to meet modeling assumptions and frequencies for categorical data to assess whether the data are sparse. With the exception of the statistical test of the primary hypothesis, all statistical tests will be two-sided and will not be adjusted for multiple comparisons. As described in greater detail below, the test of the primary hypothesis (comparing the groups with respect to proportion who are community ambulators at 16 weeks) will be based on a one-sided 0.025-level hypothesis test performed at five time points throughout the trial.

15.1 Primary Aim

The primary aim is to determine if a 16-week intervention based on aerobic conditioning, specificity of training, and muscle overload for strengthening (the PUSH intervention) is more successful in producing community ambulation at 16 weeks post-randomization than an intervention of transcutaneous electrical nerve stimulation, flexibility, and AROM exercises (the PULSE intervention). Therefore, the one-sided null hypothesis that the PUSH intervention does not result in a higher proportion of community ambulators 16 weeks post-randomization will be tested. This hypothesis will be tested at five time points based on a Z-statistic (which is equivalent to the square root of the Pearson chi-square statistic). The critical values for each time point were chosen to preserve an overall type-1 error rate of 0.025.²⁰⁶ If the exploratory analyses reveal data sparseness (expected frequency less than 5 for at least one combination of treatment group and community ambulation status), Fisher's exact test will be performed instead of using the chi-square statistic. The difference in proportions with a 95% confidence interval will also be reported.

The binary outcome variable will be ability to walk at least 300 meters in six minutes (yes/no). This variable will take the value of 'yes' if the participant was tested with the SMWT and walked 300 m or more in six minutes. This variable will take the value of 'no' if 1) the participant was tested with the SMWT and walked less than 300 m in six minutes or 2) the participant was not tested with the SMWT (or the participant was tested but not according to protocol) and adjudication resulted in the participant's being classified as a treatment failure (see 11.5 for description of the adjudication procedure). Participants whose adjudication result is 'indeterminate' will be excluded from the primary analysis.

In a secondary analysis, an alternative outcome variable will be created to represent the participant's community ambulation status at 16-week follow-up. This secondary variable will take the value of 'yes' if the participant was tested with the SMWT and walked 300 m or more in six minutes. The secondary variable will take the value of 'no' if 1) the participant was tested with the SMWT and walked less than 300 m in six minutes, 2) the participant was not tested with the SMWT and adjudication resulted in the participant's being classified as a treatment failure because of death, sickness, or gait speed < 0.6 m/s, or 3) the participant was tested with the SMWT but not according to protocol and adjudication resulted in the participant's being classified as a treatment failure, whatever the reason. The secondary variable will take the value of 'missing' if 1) the participant was not tested with the SMWT and adjudication resulted in the participant's being classified as a treatment failure based only on self- or proxy-reported walking limitation or 2) the participant was not tested with the SMWT (or the participant was tested but not according to protocol) and adjudication resulted in the participant's being classified as 'indeterminate'. All participants, including those with a missing value for the alternative outcome variable, will be included in the secondary analysis. To be consistent with the principle of ITT, weighted estimated equations (described below) will be used for this analysis.

Study site will be investigated as a modifier of the effect of the intervention by testing a site-by-intervention interaction term. If study site is an effect modifier, we will report 1) site-specific treatment effects and 2) a summary measure of treatment effect using standardization. Standardization will be accomplished using inverse probability of treatment weighting (as a function of study site) in a marginal structural model.²⁰⁷

In the fall of 2014, a decision was made to modify the frequency of intervention visits during the first 8 weeks from 3 per week to 2 per week. The number of sessions per week in the first 8 weeks will also be assessed as a potential effect modifier, using the methods described in the previous paragraph. If we find strong evidence that the number of sessions per week modifies the comparison of the intervention groups, we will report treatment effects separately for the period when there were two sessions per week and the period when there were three sessions per week.

This change in number of sessions also affords us an opportunity to assess the impact of visit frequency on the intervention outcomes as a secondary analysis. To do so, assuming no significant interaction between site and intervention group, we will assess the statistical significance of the effect of number of sessions. If there is significant interaction between number of sessions and intervention group, then we will compare the outcomes obtained during the period with two sessions per week in the first 8 weeks to those obtained during the period with three sessions per week in the first 8 weeks separately in each intervention group.

In addition, a series of analyses will be performed to examine the differential impact of the PUSH intervention relative to the PULSE intervention in subgroups defined by participant

characteristics. To do this, a variable-by-intervention interaction term will be tested for each of the following variables:

1. Gender
2. Age at baseline (≥ 85 years versus 60-84 years)
3. Baseline depression (CES-D score ≥ 16 versus CES-D score < 16)
4. Baseline balance confidence (with median Activities-Specific Balance Confidence scale score as the cutpoint to define the subgroups)
5. Baseline nutritional status (MNA[®]-SF score < 8 versus MNA[®]-SF score ≥ 8)
6. Baseline cognitive status (3MS score < 91 versus 3MS score ≥ 91)

If the interaction term for any of these subgroup variables is significant, results will be presented separately in strata of the subgroup variable.

15.2 Secondary Objectives

15.2.1 Delayed and Sustained Effects

Generalized estimating equations (GEEs)²⁰⁸ will be used to examine whether the proportion of community ambulators differs between the PUSH and PULSE interventions at 40 weeks post-randomization and, for the subset of participants who were followed for 40 weeks, whether the difference in proportions at 40 weeks changed from the difference in proportions at 16 weeks. GEE will be used for this analysis because the data are longitudinal and, unlike in likelihood-based methods, the estimates are robust to misspecification of the working model (e.g., binomial, normal, etc.). This approach accounts for intra-participant correlation between repeated measures. With the use of GEEs we will be able to relate outcomes, at specific time points, to treatment group. For all analyses using GEE, the empirical variance estimate will be used because it is robust to model misspecification. The longitudinal model for this aim will be fit using a binomial working model and is expressed by the equation:

$$\text{Logit}(p) = a + b_1 X + b_2 t_{40} + b_3 X t_{40}, \quad (\text{Eq. 1})$$

where p is the probability of a particular outcome, $\text{Logit}(p) = \ln(p/(1-p))$, X is the intervention indicator (1/0) variable; b_1 is the treatment effect at 16 weeks; t_{40} is the 40-week follow-up time post-randomization indicator (0=16 weeks; 1=40 weeks); and $X t_{40}$ is the intervention-by-time interaction variable. The fitted coefficients in Eq.1 provide estimates of the proportion of community ambulators in the PUSH vs PULSE interventions at 16 and 40 weeks post-randomization. To test the null hypothesis of equal proportion of community ambulators in both groups at 40 weeks post-randomization, we will test the null hypothesis $H_0: (b_1+b_3)=0$ using a two-sided test with type I error of 0.05. This test will be performed regardless of results from the primary aim. However, the interpretation of results from this test will depend on those from the primary aim. If there is evidence for a difference in proportion of community ambulators at 16 weeks, then rejecting this hypothesis can be interpreted as evidence for a sustained effect of the PUSH intervention on community ambulation at 40 weeks; if there is no evidence for a difference in proportion of community ambulators at 16 weeks, then rejecting this hypothesis can be interpreted as evidence for a delayed effect of the PUSH intervention on community ambulation at 40 weeks. We are also interested in describing the trends in community ambulation from 16 to 40 weeks post-randomization in both groups. To assess the null hypothesis of no change in the between-group difference of proportion of community ambulators between 16 and 40 weeks post-randomization, we will test the null hypothesis $H_0: b_3=0$ using a Wald chi-square test with type I error of 0.05. All treatment effects will be reported with their respective 95% confidence intervals.

A similar approach will be used to examine delayed and sustained effects for the secondary and

tertiary outcomes described below.

15.2.2 Secondary and Tertiary Outcomes

Secondary outcomes include five variables (endurance, dynamic balance, walking speed, quadriceps strength, and lower extremity function) that are hypothesized to be precursors to community ambulation. In addition, we will examine the difference between the treatments with respect to the following tertiary outcomes: ADLs, balance confidence, quality of life, physical activity, lower extremity physical performance, depressive symptoms, increase of ≥ 50 meters in distance walked in six minutes, cognitive status, and nutritional status. GEE will be used to compare the PUSH and PULSE interventions at 16 and 40 weeks post-randomization. Increase of ≥ 50 m in distance walked, a dichotomous outcome, will be analyzed using the same method as the primary outcome. All of the other secondary and tertiary outcomes are continuous; therefore, a normal working model will be used to estimate the parameters in the following equation:

$$\mu = a + b_1 X + b_2 t_{16} + b_3 t_{40} + b_4 X t_{16} + b_5 X t_{40}, \quad (\text{Eq. 2})$$

where μ is the mean of a particular outcome, X is the intervention indicator (1/0) variable; t_{16} and t_{40} are the 16- and 40-week follow-up time post-randomization indicators, respectively; and $X t_{16}$ and $X t_{40}$ are the intervention-by-time interaction variables. This model accounts for outcomes at three time points: baseline, 16 weeks, and 40 weeks post-randomization. By treating the baseline value as an outcome, we quantify mean changes in the outcome relative to baseline levels. Differences between the two groups in changes from baseline to 16 and 40 weeks post-randomization will be compared using Eq. 2 by testing $H_0: b_4=b_5=0$ using a Wald chi-square test with type-I error of 0.05. All treatment effects will be reported with their respective 95% confidence intervals.

15.2.3 Cost-Effectiveness of Interventions

To assess the cost-effectiveness of study interventions, the EEC will conduct analyses of within-trial comparisons for the economic endpoints (resource utilization/costs and SF-6D/QALYs) and will also undertake a model-based analysis that allows the economic value of both study interventions to be assessed relative to usual care. Longitudinal modeling appropriate for repeated measures data will be used to make inferences on the overall differences in cost and QALYs associated with the study interventions. The basic statistical analyses of cost and QALYs will be similar to the approach described for other study endpoints, but will be undertaken in the EEC in close collaboration with the DCC.

Statistical analyses of SF-6D will produce an estimate of the incremental QALYs associated with the PUSH intervention at each time point where SF-36 is measured. The estimated difference in QALYs attributable to the PUSH intervention will be estimated by taking a time-weighted average of the time-specific intervention effects. Statistical analyses of cost data, which will be adjusted to a constant dollar year (e.g., 2012 US dollars), will produce an estimate of the incremental costs associated with the PUSH vs. PULSE intervention.

The incremental cost-effectiveness ratio (ICER), which is defined as the net change in cost divided by the net change in effectiveness (QALYs) when interventions are ranked in order of increasing cost, is the focus of the economic analysis. When estimated as added cost per QALY gained, the ICER allows the value of interventions in hip fracture to be compared with interventions in other diseases. ICERs will be estimated using both the statistical analysis of cost and QALY data (i.e., trial-based ICER) and a model-based analysis that combines trial results with other existing data (i.e., model-based ICER). The trial-based ICER addresses the economic value of the PUSH intervention relative to the PULSE, while the model-based ICER

estimates the economic value of the study interventions relative to usual care (as described below).

The second objective of the cost-effectiveness analysis is to develop and implement a decision-analytic modeling framework that will incorporate within-trial findings regarding costs and QALYs for the purpose of evaluating the cost-effectiveness of the PUSH intervention and PULSE relative to usual care. Model-based analyses are commonly employed to extend or augment clinical trials because the cost of trials precludes study of all interventions of interest and because it is often desirable to consider the value of interventions over a longer time horizon than what is observed in the trial. To make inferences about the economic value of the study interventions relative to usual care, a Markov state-transition modeling framework that incorporates trial results will be developed and utilized. Estimates of the cost of the study interventions will be derived from time estimates recorded in the field over the course of the study. Estimates of the QALY impact of usual care will be derived from existing hip fracture cohorts (control arms of other trials). Estimates of changes in SF-6D for similar patient groups are available from the control arms of BHS RCTs. Because these studies have tracked resource utilization with few questions and follow up measures, extensive sensitivity analyses that vary the impact of the interventions on resource utilization will be undertaken to characterize the magnitude of change in costs that would be required to qualitatively affect the conclusions of the economic analysis.

The model-based ICER for the study interventions relative to usual care will be compared qualitatively with the costs per additional QALY estimates of other commonly accepted medical interventions. Uncertainty in the model-based analysis will include estimation of cost-effectiveness acceptability curves, which represent the probability that a particular cost-effectiveness threshold (e.g., \$100,000 per QALY gained) is achieved when variability in cost and QALYs is considered in probabilistic sensitivity analyses.

15.3 Missing Data

By design, there will be no missing data at baseline because only participants with complete baseline data will be randomized. At follow-up, scores for scales that have published rules for handling missing scale items (e.g., the CES-D and the SF-36) will be calculated using those rules. All other scales will be considered missing if any part of the scale is missing. To correct for potential selection bias from missing data, we will perform a weighted estimating equations (WEE) analysis.²⁰⁹ This method involves two steps. First the probability of being observed (not missing) is calculated as a function of predictors of missingness. Next the relationship of treatment group to outcome is assessed using the inverse probability of being observed as a weight in the GEE model. WEEs are advantageous because a) they are consistent with the ITT principle because participants with missing data are included in the analysis through the estimated weight, and b) unlike other methods for addressing missing data, they can be performed in conjunction with marginal structural modeling by multiplying both weights together.

15.4 Nonadherence

In the presence of nonadherence, ITT analyses have the benefit of conservatively estimating effects. However, ITT analyses may miss true effects because their results are biased toward the null. To address this issue, we will examine adherence (defined as proportion of intervention visits completed) in both intervention groups. If adherence is less than 80% in either group, we will perform a secondary analysis adapting marginal structural modeling to address noncompliance. In this case, the weight will be the inverse probability of treatment received as a function of treatment assignment and factors that may affect treatment compliance. This method has the benefit of accounting for intermediary factors that may impact compliance without

distorting the randomization by conditioning on these factors (i.e., a marginal analysis rather than a conditional analysis). Precedents for this approach are available in the literature by Cook.²¹⁰

15.5 Interim Analyses

Interim analyses will be conducted by an alpha and lower bound spending design. At the time of this update, we have already performed an interim analysis based on the first 28.6% of the data. We plan to perform three additional interim analyses (based on the first 40%, 60%, and 80% of data available), where the boundary values for early stopping will be evaluated using the Hwang-Shih-Decani spending function approximation to the O'Brien-Fleming alpha-spending function [$\gamma = -4$ for lower-bound alpha spending (inefficacy/harm), and $\gamma = 4$ for upper-bound alpha spending (efficacy)].^{211,212} The upper and lower bounds will be computed for a test of efficacy with one-sided nominal $\alpha = 0.025$. For example, when testing for efficacy ($\delta > 0$) at the first interim analysis, $Z > 3.09$ would denote efficacy, and $Z < -1.76$ would denote inefficacy/harm. Table 4 shows the anticipated proportion of the sample accrued at each of the remaining interim analyses along with the corresponding critical values for declaring significance (or lack thereof) at each time point. The critical values are subject to change if the actual information available at the time of the analysis differs from the expected information available. These critical values were calculated using the gsDesign package in R version 2.10.1.

Table 4. Anticipated Critical Values for Each Planned Analysis

Analysis	Expected % of information available	Critical z-value for upper-bound alpha spending (for efficacy)	Critical z-value for lower bound alpha spending (for inefficacy/harm)
First interim analysis	28.6%	3.09	-1.76
Second interim analysis	40%	3.03	-1.57
Third interim analysis	60%	2.69	-0.97
Fourth interim analysis	80%	2.37	-0.21
Final analysis	100%	2.03	2.03

The spending function applies specifically to analysis of the primary outcome (community ambulation at 16 weeks post-randomization). However, at each interim analysis, study performance and secondary and tertiary outcomes will be examined to aid in the interpretation of the primary outcome results.

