Using a group sequential design with four interim analyses (see Section 15.5), and assuming an overall loss to follow-up of 6.8% and treatment non-compliance of 12.2%, a total sample of 210 enrolled patients (105 patients per group) is sufficient to achieve over 80% power for the detection of a 20 percentage point difference between the groups, with 16% achieving the 300 m threshold of the SMWT in the PULSE group vs 36% in the PUSH group, using a one-sided 0.025 significance level. The power specified is for the detection of a time-specific difference at the 16-week follow-up. This calculation accounts for the sample size inflation of 2.4% needed to account for the group sequential design^{211,212} and for the impact of noncompliance on the variance of treatment differences under the assumption that non-compliers assigned to the PUSH group have an equal 16-week proportion achieving community ambulation as participants assigned to the PULSE group.^{214,215}

Table 5 shows the power to detect various between-group differences in proportions of community ambulators using a one-tailed test of the difference in proportions at the 2.5% significance level. The table indicates that the study has adequate power for detecting differences down to 20 percentage points.

Table 5. Power to Detect Difference in Proportions

True Difference in Proportion Achieving Community Ambulation at 16 Weeks	Power (%)
23 percentage points	89
22 percentage points	87
21 percentage points	84
20 percentage points	80
19 percentage points	76
18 percentage points	72
17 percentage points	68

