1.1 Primary Outcome

1.1.1 Primary Analysis of Primary Outcome.

The primary aim is to determine if a 16-week intervention based on aerobic conditioning, specificity of training, and muscle overload for strengthening (the PUSH intervention) is more successful in producing community ambulation at 16 weeks post-randomization than an intervention of transcutaneous electrical nerve stimulation, flexibility, and AROM exercises (the PULSE intervention). Therefore, the one-sided null hypothesis that the PUSH intervention does not result in a higher proportion of community ambulators 16 weeks post-randomization will be tested. This hypothesis will be tested at five time points based on a Z-statistic (which is equivalent to the square root of the Pearson chi-square statistic). The critical values for each time point were chosen to preserve an overall type-1 error rate of 0.025. Table 1 shows the critical values:

Table 1. Critical Values for Each Planned Analysis

Analysis	Expected % of information available	Critical z-value for upper-bound alpha spending (for efficacy)	Critical z-value for lower bound alpha spending (for inefficacy/harm)
First interim analysis	28.6%	3.09	-1.76
Second interim analysis	40%	3.03	-1.57
Third interim analysis	60%	2.69	-0.97
Fourth interim analysis	80%	2.37	-0.21
Final analysis	100%	2.03	2.03

If the exploratory analyses reveal data sparseness (expected frequency less than 5 for at least one combination of treatment group and community ambulation status), Fisher's exact test will be performed instead of using the chi-square statistic. A 95% confidence interval will be constructed for the probability of community ambulation in each group by inverting two one-sided tests based on the binomial distribution. If the primary analysis p-value is based on the Z-statistic, then a confidence interval for the difference in community ambulation between the two groups will be constructed using standard asymptotic methods. If the primary analysis is based on Fisher's exact test, then an exact 95% confidence interval will be constructed for the difference in probabilities using the method of Chan and Zhang (Chan ISF, Zhang Z 1999) as implemented in SAS.

The binary outcome variable will be ability to walk at least 300 meters in six minutes (yes/no). This variable will take the value of 'yes' if the participant was tested with the SMWT and walked

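### Protocol 15.5 gives gamma = 4 for the efficacy bound, but the printed critical values, inflation and power come from gamma = -4, so a bound recalculated from the text would be wrong

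*Protocol*

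**What the plan says.** Protocol section 15.5 sets the stopping bounds by a "Hwang-Shih-Decani spending function approximation to the O'Brien-Fleming alpha-spending function". It gives two parameters: "\gamma = -4$ for lower-bound alpha spending (inefficacy/harm)" and "and $\gamma = 4$ for upper-bound alpha spending (efficacy)". The level is set by "The upper and lower bounds will be computed for a test of efficacy with one-sided nominal $\alpha = 0.025".

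Table 4 of the protocol lists these bounds:

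| Look | Information | Efficacy | Inefficacy/harm |
|---|---|---|---|
| 1 | 28.6% | 3.09 | -1.76 |
| 2 | 40% | 3.03 | -1.57 |
| 3 | 60% | 2.69 | -0.97 |
| 4 | 80% | 2.37 | -0.21 |
| Final | 100% | 2.03 | 2.03 |

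The first look has been done: "At the time of this update, we have already performed an interim analysis based on the first 28.6% of the data". The remaining values are provisional: "The critical values are subject to change if the actual information available at the time of the analysis differs from the expected information available".

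Protocol section 15.6.1 builds the power calculation on a "sample size inflation of 2.4% needed to account for the group sequential" design and reports 80% power for a 20-point difference with 210 participants. SAP section 1.1.1 repeats the same bounds under "Table 1. Critical Values for Each Planned Analysis" but names no spending function and no gamma.

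**The concern.** In this family a negative gamma holds alpha back for the end, as O'Brien-Fleming does, and a positive gamma spends it early. With gamma = +4, about 69% of the 0.025 (0.01735) would be spent at the first look. That contradicts the description in the same sentence and the first-look bound of 3.09 worked out just after it.

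Either the table or the parameter had to be wrong. If the table were wrong, the sample size and power would fall with it. If only the parameter is wrong, the danger lies in recalculation. The protocol expects bounds to move with actual information, and the change log for Version 9.0 shows that they were already revised once, when the target sample size was cut. A statistician who enters the printed parameter would get an interim hurdle far too low and a final hurdle too high.

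**Working it through.** **Inputs.** From Protocol 15.5: information fractions 0.286, 0.4, 0.6, 0.8 and 1, and one-sided alpha 0.025. From Protocol 15.6.1: 105 per group, 16% vs 36%, 6.8% loss to follow-up, 12.2% non-adherence, and PUSH non-adherers responding at the PULSE rate.

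**Spending function.** Cumulative spend at information t is f(t) = a(1 - exp(-gamma t)) / (1 - exp(-gamma)). Here a = 0.025 for the upper bound and a = 0.975 for the lower bound, both under the null. Bounds were solved by recursive numerical integration of the sequential test statistic.

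**Step 1: reproduce Table 4.**

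| | Look 1 | Look 2 | Look 3 | Look 4 | Final |
|---|---|---|---|---|---|
| Efficacy, printed | 3.09 | 3.03 | 2.69 | 2.37 | 2.03 |
| Efficacy, gamma = -4 | 3.091 | 3.032 | 2.693 | 2.374 | 2.025 |
| Efficacy, gamma = +4 | 2.11 | 2.41 | 2.50 | 2.68 | 2.86 |
| Alpha spent, gamma = -4 | 0.0010 | 0.0018 | 0.0047 | 0.0110 | 0.025 |
| Alpha spent, gamma = +4 | 0.01735 | 0.02032 | 0.02316 | 0.02443 | 0.025 |

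The lower bounds under gamma = -4 are -1.76, -1.566, -0.967 and -0.208, all as printed. Under gamma = +4 the first lower bound would be +0.46. Both columns therefore need -4 under the same function, and no sign convention makes a bracket with opposite signs correct. Treating the lower bound as binding, non-binding or absent does not rescue +4.

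**Step 2: inflation and sample size.** Inflation is (drift needed for the target power / (z for 0.975 + z for power)) squared. With gamma = -4 it is 2.5% at 80% power and 2.3% at 90%, against the stated 2.4%. With gamma = +4 from look 1 it is 48.9% at 80% power.

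- Adherence-diluted PUSH rate: 0.16 + 0.878 x 0.20 = 0.3356.
- Fixed-design requirement: 94 per group.
- Stated inflation: 94 x 1.024 = 96.3, rounded up to 97; 97 / 0.932 = 104.1, rounded up to 105 per group, or 210. This is the stated figure.
- Under +4: 94 x 1.4894, rounded up to 141; 141 / 0.932 = 151.3, rounded up to 152 per group, or 304.

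**Step 3: power.** Evaluable n is 105 x 0.932 = 97.86 per group. The pooled rate is (0.3356 + 0.16)/2 = 0.2478. The drift is 0.1756 / sqrt(2 x 0.2478 x 0.7522 / 97.86) = 2.845 with pooled variance, or 2.906 unpooled. Each range below runs from pooled to unpooled.

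The printed bounds give 80.1% to 81.8% power and one-sided type I error 0.0248. Across differences of 23 down to 17 points, pooled power is 88.8, 86.3, 83.4, 80.1, 76.4, 72.4 and 68.0%. Protocol Table 5 states 89, 87, 84, 80, 76, 72 and 68. Using +4 from look 1 would leave 62-64% power at 20 points.

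**Step 4: what recalculating with +4 would do.** Earlier looks keep their printed bounds.

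| +4 applied from | Resulting bounds | Power | Type I error |
|---|---|---|---|
| Look 2 | 2.05 / 2.43 / 2.64 / 2.83 | 64-66% | 0.025 |
| Look 3 | 2.00 / 2.51 / 2.75 | 68-70% | 0.025 |
| Look 4 | 1.99 / 2.58 | 74-76% | 0.025 |
| Final only | 2.03 | 80-82% | 0.025 |

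As an example of a look that misses its target, look 2 at 45% information gives a bound of 2.93 under -4 but 2.03 under +4.

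If a single interim bound were replaced by its +4 value and all the others left as printed, type I error would be 0.038 (look 2), 0.036 (look 3) or 0.033 (look 4).

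**The case against.** The arithmetic is not in dispute. The case against concerns weight.

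- **The sign may have been lost when the PDF was read.** This cannot be excluded from the text alone. The minus sign on the other parameter in the same bracket survived, which makes it less likely. The sponsor can settle it at once, and the SAP would still lack a spending function.
- **The error largely exposes itself.** The O'Brien-Fleming description, the worked first-look example and the printed table all point to -4. A bound of 2.05 following 3.09 should raise questions. This lowers the chance of misuse, but the bracket remains the only place where a parameter is stated.
- **The harm needs several steps.** A look must miss its planned fraction, the bound must be recalculated from the bracket, and nobody must compare it with the table. This stands. Keeping the printed bounds is also safe under modest departures: with look 2 at 35% or 45%, or looks 3 and 4 at 65% and 85%, type I error is 0.0242 to 0.0249.
- **The inflated type I error comes from a mixed procedure that neither document describes.** This also stands. Consistent use of +4 at all remaining looks holds 0.025. The cost of following the written rule is lost power and an early hurdle that is too easy; the figures of 0.033 to 0.038 are hypothetical.
- **The 2.4% is not an exact match.** True: it lies between the 80% and 90% power values under -4. It is nowhere near the 49% that +4 requires.

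**Conclusion.** The point holds. The efficacy parameter printed in Protocol 15.5 is inconsistent with the design, while the critical values in Protocol Table 4 and SAP Table 1, the sample size of 210 and the stated power are all consistent with gamma = -4 for both bounds.

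Any analysis that uses the printed bounds unchanged is unaffected. The consequence is confined to recalculated interim bounds: the worst case, +4 from look 2, loses about 16 percentage points of power (80-82% down to 64-66%) and lowers that look's hurdle by about one unit of Z. The power figures assume the protocol's own response rates, loss and non-adherence, with look 1 kept at 3.09 as already performed. The error should be fixed because it sits in the only stated recalculation parameter, but it is not a flaw in the design itself.

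**What to change.** In Protocol 15.5, state gamma = -4 for both the inefficacy/harm bound and the efficacy bound. Beside SAP Table 1, add one sentence naming the Hwang-Shih-DeCani spending function with gamma = -4 for both bounds, so that any recalculated value uses the function that produced the table.

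The cost is one sign in the protocol and one sentence in the SAP. Critical values, sample size and power stay as they are.
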